5.6.2.2 Adverse events summaries

The number and percentage of participants who experience AEs will be summarized by treatment group. The following outputs will be created:

- Incidence of TEAEs (defined as the number and percentage of participants with at least one TEAE (incidence proportion) – Overview. The following categories will be included by treatment arm:
 - Any TEAEs
 - Serious TEAEs
 - Participant discontinuation due to TEAEs (defined as TEAEs with “Did the Adverse Event Lead to Dropout ticked” as “Yes”)
 - Permanent withdrawal of IMP due to TEAEs (defined as TEAEs with an action taken with study medication of “drug permanently withdrawn”)
 - Temporary withdrawal of IMP due to TEAEs (defined as TEAEs with an action taken with study medication of “drug temporarily interrupted”)
 - Treatment-related TEAEs
 - Severe TEAEs

All Deaths (AEs leading to death). Note: Above TEAEs will be summarized to capture the overall and by MedDRA Primary SOC (PSOC), Higher level term (HLT) and PT. Additionally, the frequency of TEAEs will be summarized by MedDRA PSOC and PT.

- The number, percentage of participants and frequency of the following TEAEs will be summarized by SOC, HLT and PT for:
 - Incidence of any TEAEs
 - Incidence of Serious TEAEs
 - Incidence of Permanent withdrawal of IMP due to TEAEs
 - Incidence of Any TEAEs by Maximum Intensity (mild, moderate and severe) Incidence of Any TEAEs by Relationship
 - Incidence of Any TEAEs by Event Outcome
 - Incidence of any TEAE's per 100 Patient years.

AESIs are the cases of potential Hy's Law (see [Section 6.1.9](#)).

AESMs or AESIs will be identified based on the assessment by the Investigator as recorded in the CRF. An AE will be counted as an AESMs or AESIs if there is a 'yes' response to the question "Adverse Event of Special Interest or Event of Special Monitoring?" and not otherwise. These flags will be included in the listings.

When applicable, adverse event summaries will be ordered by alphabetical SOC, alphabetical HLT within SOC and decreasing frequency of PT in the rozanolixizumab total column for tables.

Listings of all AEs, permanent withdrawal of IMP due to AEs, participant discontinuation from study due to AEs, and AEs leading to death will be presented by treatment group.

5.6.3 Additional Safety Assessments

5.6.3.1 Clinical laboratory evaluations

The following [Table 5](#)– lists safety laboratory assessments that are collected throughout the study:

Table 5–9: Clinical Laboratory Parameters

Laboratory Assessments	Parameters		
Hematology	Platelet Count	RBC Indices:	WBC Count with Differential:
	Red Blood Cell (RBC) Count	Mean corpuscular volume (MCV)	Neutrophils
	Hemoglobin	Mean corpuscular hemoglobin (MCH)	Lymphocytes
	Hematocrit	%Reticulocytes	Monocytes
			Eosinophils
			Basophils

Laboratory Assessments	Parameters			
Clinical Chemistry	Blood urea nitrogen (BUN)	Potassium	Aspartate Aminotransferase (AST) / Serum Glutamic-Oxaloacetic Transaminase (SGOT)	Total and direct bilirubin
	Creatinine	Sodium	Alanine Aminotransferase (ALT) / Serum Glutamic-Pyruvic Transaminase (SGPT)	Total Protein
	Glucose (non-fasting)	Calcium	Alkaline phosphatase	Albumin
	Lactate dehydrogenase (LDH)	C-reactive protein (CRP)	Low-density lipoprotein (LDL) High-density lipoprotein (HDL) Total cholesterol Triglycerides	
Routine Urinalysis	
 Specific gravity pH, glucose, protein, blood, ketones, bilirubin, urobilinogen, nitrite, leukocyte esterase by dipstick Microscopic examination (if blood or protein is abnormal) 			
Other Screening Tests	
 Follicle-stimulating hormone (FSH) and estradiol (as needed in women of non-childbearing potential only) Serum or urine alcohol and drug screen (to include at minimum: amphetamines, barbiturates, cocaine, opiates, cannabinoids and benzodiazepines) Serum (at Screening) or urine (all other visits) human chorionic gonadotropin pregnancy test (as needed for women of childbearing potential)^a Serology testing (for Hepatitis A, Hepatitis B, Hepatitis C, and HIV) 			

Note: The tests detailed in the table will be performed by the central laboratory. Local laboratory results are only required in the event that the central laboratory results are not available in time for either study treatment administration and/or response evaluation.

^a IGRA, TB and Dipstick uri-analysis and urine pregnancy dipstick tests will be performed locally.

Chemistry, hematology and quantitative urinalysis (observed value, absolute change from Baseline) will be listed in standard unit by treatment group at each scheduled visit.

All lab data will be used for the listings.

Measurements BLQ will be imputed with half of the lower limit of quantification LLOQ for the purpose of calculating change from Baseline. Measurements ALQ will be imputed to the upper

quantification limit for the purpose of any quantitative individual participant data. These rules will be applied to all safety laboratory data including clinical chemistry and urinalysis.

All central and local laboratory test results will be listed using the SS, including Baseline, scheduled and unscheduled visits with results in standard unit. Values outside the reference range for the continuous variables and any MA values will be flagged in the listings. The reference ranges will also be reported in the listings. Additional lab test, including pregnancy testing, will be listed separately.

5.6.3.2 Potential drug-induced liver injury (pDILI)

The number and percentage of participants who meet one or more of the following pDILI criteria will be summarized by treatment group at any visit (including unscheduled visit):

- Participants with at least one post-Baseline liver laboratory assessment
- Incidence of potential hepatotoxicity with symptoms potentially associated with hepatitis or hypersensitivity
- Incidence of potential hepatotoxicity with no symptoms potentially associated with hepatitis or hypersensitivity
- Laboratory criteria for pDILI:
 - (AST or ALT $\geq 3 \times$ ULN) and TBL $\geq 1.5 \times$ ULN
 - (AST or ALT $\geq 3 \times$ ULN) and TBL $\geq 2 \times$ ULN
 - (AST or ALT $\geq 3 \times$ ULN) and TBL $\geq 2 \times$ ULN and ALP $< 2 \times$ ULN (Hy's Law)

In order to meet the above criteria, a study participant must experience the elevation in bilirubin and ALT or AST (and the absence of the ALP elevation) at the same visit. For example, a study participant who experiences a $\geq 2 \times$ ULN elevation of bilirubin at one visit and a $\geq 3 \times$ ULN elevation in ALT (or AST) at a subsequent visit has not fulfilled the Hy's law criteria. If participant meets part of one criterion but at least one parameter is unknown, then he/she should not be considered for meeting the criterion.

Additional analyses for liver function tests (LFTs) will be performed to assess the potential for liver toxicities in accordance with the United States Food and Drug Administration guidelines. Per guidelines, the following criteria will be used to define levels of LFT elevation:

- Aspartate aminotransferase (AST): $>3 \times$ ULN, $>5 \times$ ULN, $>8 \times$ ULN, $>10 \times$ ULN, $>20 \times$ ULN
- Alanine aminotransferase (ALT): $>3 \times$ ULN, $>5 \times$ ULN, $>8 \times$ ULN, $>10 \times$ ULN, $>20 \times$ ULN
- AST or ALT: $>3 \times$ ULN, $>5 \times$ ULN, $>8 \times$ ULN, $>10 \times$ ULN, $>20 \times$ ULN
- Total bilirubin (TBL): $>1.5 \times$ ULN, $>2 \times$ ULN
- Alkaline phosphatase (ALP) $>1.5 \times$ ULN

The number and percentage of study participants who meet one or more of the above LFT elevation criteria will be summarized by treatment group at any visit (including unscheduled visit).

A listing will also be provided for study participants who meet at least one of the above criteria. All results obtained at that visit for the specified parameters will be displayed.

5.6.3.3 Vital Signs

A by-participant listing of all vital sign measurements and change from Baseline will be presented by treatment group and timepoint. The listing will include a flag for values identified as MA outlined in Section 6.5.

Repeated and unscheduled measurements will be handled as described in [Section 6.1.7.2](#).

5.6.3.4 12-Lead Electrocardiograms (ECG)

The following 12-Lead ECG variables will be listed if the data is available. (NB. These assessments were removed from protocol amendment 4).

- Heart rate
- PR interval
- RR interval
- QRS duration
- QT interval
- QT corrected for heart rate using Fridericia's formula ($QTcF = QT/RR^{1/3}$)

A listing of electrocardiogram data will be presented, including repeated and unscheduled measurements. Electrocardiogram findings for the individual triplicate measurements will be listed separately.

5.6.3.5 Physical examination

Data from the Physical Examination are provided in subject data listings presented by treatment group, subject and visit, displaying all data collected for all subjects. No summaries will be provided. Findings that are considered clinically significant will be reported as AEs.

5.6.3.6 Neurological examination

Data from the Neurological Examination are provided in subject data listings presented by treatment group, subject, and visit, displaying all data collected for all subjects. No summaries will be provided. Findings that are considered clinically significant will be reported as AEs.

5.6.3.7 Childbearing potential

Childbearing potential will be collected at Screening. A by participant listing will be provided using the RS.

5.6.3.8 Assessment and management of Tuberculosis (TB)

[figure not shown]
Results of the interferon gamma release assay (IGRA) TB test, chest X-ray and TB signs and symptoms questionnaire for TB will be listed.

5.6.3.9 Headache questionnaire

The results of the headache questionnaire will be listed for each participant.

5.6.3.10 Suicidal risk monitoring

Suicidal ideation is defined as an event in any of the following 5 categories:

Suicidal behavior is defined as an event in any of the following 5 categories:

Suicidal behavior or ideation is defined as an event in any of the above 10 categories.

Self-injurious behavior without suicidal intent is corresponding to the response to [REDACTED] in questionnaire.

A by-participant listing of the C-SSRS questionnaire data will be provided by treatment group if this data is reported by any participant in the study

5.7 Other Analyses

5.7.1 Other endpoints and/or parameters

All analyses described in [Section 5.7.1.1](#) will be performed on the RS, and all other analyses will be performed on Safety set.

5.7.1.1 Pharmacokinetics

5.7.1.1.1 Rozanolixizumab

All analyses described in this section will be based on the RS.

Individual plasma concentrations of rozanolixizumab will be summarized by scheduled sampling day for the RS on an individual participant basis due to the low participant numbers.

- Scatter dot plot of individual rozanolixizumab postdose plasma concentrations categorized by Day (Days 3, 5, 164, 166) with all days in the same plot.

The following rules will apply for PK data listings and summaries:

- Values below the LLOQ will be reported as below the limit of quantification (BLQ)
- Descriptive statistics of concentrations will be calculated if at most 1/3 of the individual data points at a timepoint are missing or are not quantifiable (<LLOQ). Values that are BLQ will be replaced by the numerical value of the LLOQ/2 in this instance. If more than 1/3 of the

individual data points at a timepoint are missing or are not quantifiable, then only n, minimum, median and maximum will be presented. The other descriptive statistics will be left blank.

- If n<3, then only the n, minimum and maximum will be presented. If no study participants have data at a given timepoint, then only n=0 will be presented.
- The 95% CI lower and 95% CI upper should be left blank if the SD (or equivalently, the geoCV) is 0
- The geoCV will be calculated using the following formula where SD is the standard deviation from the log-transformed data

$$\text{geoCV}(\%) = \sqrt{\exp(\text{SD}^2) - 1} \times 100.$$

Individual concentrations of rozanolixizumab will be listed for the RS and will include the actual sampling time in days relative to the previous dose and the IgG observed at the same visit, for the same visit, IgG and IgG subclasses by achievement of primary endpoint of seizure freedom (yes/no).

5.7.1.2 Pharmacodynamics

All analyses described in this section will be based on the RS.

5.7.1.2.1 Total serum Immunoglobulin G (IgG) and IgG subclasses

Total serum IgG concentrations will be summarized by treatment group and time point for observed values, change from Baseline, and percentage change from Baseline.

The maximum absolute and percentage decrease from Baseline in total serum IgG and IgG subclasses will be summarized for each treatment. In the event that a decrease from Baseline is not observed in a given participant, the maximum decrease will be reported as the smallest increase from Baseline.

The following plots will be generated:

- Geometric mean change from Baseline values in total serum IgG, IgG subclasses over time by treatment group, with all PD endpoints and treatment groups overlaid on the same plot.
- Spaghetti plots for absolute IgG over time stratified by treatment group.
- Serum concentrations of total IgG and IgG subclasses will be listed together with concentrations of rozanolixizumab, LGI1 serum and CSF levels by achievement of primary endpoint of seizure freedom (yes/no), as specified in [Section 5.7.1.1](#).

5.7.1.2.2 Serum concentrations of [REDACTED] will be listed together with concentrations of rozanolixizumab, LGI1 serum and CSF levels by achievement of primary endpoint of seizure freedom (yes/no), Leucine-Rich Glioma Inactivated 1 (LGI1) autoantibody levels

LGI1 autoantibody serum levels will be summarized at scheduled visit for observed values, absolute and percentage changes from Baseline. Same summary will be repeated for LGI1 autoantibody CSF levels for consenting participants. Individual participant will be plotted representing percentage change from Baseline in LGI1 autoantibody serum levels, total IgG,

IgG1 and IgG4 with all endpoints in the same plot and indication of dosing time points and flag if dosing was missed. The sub-title of the graph will include achievement of primary endpoint of seizure freedom (yes/no).

LGI1 autoantibody serum levels and CSF levels will be listed, together with total IgG, IgG subclasses as described in [Section 5.7.1.2.1](#).

It should be noted that these summaries and plots will not be produced for the CSR as the data will not be available.

5.7.1.3 ADA will not be performed or evaluated in this study. Immunology

All analyses described in this section will be based on the SS.

Serum complements levels and plasma complement levels Serum [REDACTED] and plasma ([REDACTED]) complement variables will be listed by visit and time point including changes from Baseline. Descriptive summaries will be presented for both absolute values and changes from Baseline for all participants, and separately for participants who experience an infusion reaction or hypersensitivity reaction at site. The selection criteria of infusion reaction or hypersensitivity reaction are described in [Section Error! Reference source not found.](#)

Measurements BLQ will be imputed with half of the LLOQ for the purpose of calculating change from Baseline. Measurements above the limit of quantification (ALQ), if applicable, will be imputed to the upper limit of quantification.

5.7.1.4 Healthcare resource utilization

The following data, if it is available, will be listed by treatment group on the RS. a:

- Number of participants with hospitalization/ ER visit
- Total number of hospitalization/ ER visit
- Reason of hospitalization/ ER visit
- Number of participants discharged from hospitalization/ ER visit
- Total number of days in hospitalization/ ER visit, calculated as follow:

Note: /

- Total number of days in hospitalization/ ER visit = Discharge date – hospitalization/ER visit date +1. If a participant does not have discharge date, last available visit date will be used.
- Only hospitalization started after first IMP and before last visit will be considered in the summary.
- In case of missing or incomplete discharge date, the following imputation rules will be applied:
 - Hospital start date of next hospital stay – 1 as end date of this hospital stay;
 - Death date in case subject died and previous case does not apply;
 - Last visit date if previous cases do not apply.

A listing will be provided for the hospitalization/ ER visit.

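### SAP 5.7.1.4 gives two conflicting end dates for a hospital stay with no discharge date; they differ only when there is a later stay or a death.

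*SAP*

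**What the plan says.** SAP 5.7.1.4 lists hospitalization and ER data by treatment group and adds a note on how to derive the days. Three parts of the note matter.

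- **Duration bullet.** It defines "Total number of days in hospitalization/ ER visit = Discharge date" minus the admission date plus 1, and continues: "If a participant does not have discharge date, last available visit date will be used". No condition or exception is attached.
- **Inclusion bullet.** "Only hospitalization started after first IMP and before last visit will be considered in the summary".
- **Imputation bullet.** "In case of missing or incomplete discharge date, the following imputation rules will be applied": first "Hospital start date of next hospital stay", less one day, "as end date of this hospital stay"; second, "Death date in case subject died and previous case does not apply"; third, "Last visit date if previous cases do not apply".

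The number and duration of disease-related hospitalizations is an exploratory endpoint in Protocol Section 3 and SAP 1.1. Protocol 8.10 also names total days or length of stay among the data to be collected.

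**The concern.** A stay with no discharge date triggers both the duration bullet and the imputation bullet, and the SAP does not say which governs. Two programmers, each following one of them literally, would report different durations for the same record whenever the participant was admitted again or died.

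Under the duration bullet, the open stay runs to the last visit. It then covers any later admission, whose days are counted a second time, and any time spent at home. The duration part of the endpoint would then depend on which sentence was programmed.

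**Working it through.** The SAP states no figure for hospital days, so there is none to reproduce. The check applies the SAP's own formula, end minus start plus 1, under each rule. Rule 1 is the duration bullet and Rule 2 is the three-step imputation bullet.

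**Inputs.** The documents contain no hospitalization data, so all admission, discharge and death dates below are assumptions. So are the early last-visit dates in the death cases. Day 218 stands for the End of Study visit of a participant who completes treatment. The dosing interval is 7 ± 2 days (Protocol Table 1-1, footnote l). With 24 weekly doses starting on Day 1, the last falls on Day 1 + 23 × 7 = 162. The End of Study visit is 8 weeks after the final dose (SAP 1.2), which gives 162 + 56 = 218.

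**No later stay, no death.** Admission Day 100, last visit Day 218. Both rules use the last visit date: 218 − 100 + 1 = 119 days. There is no conflict.

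**Later stay.** Last visit is Day 218 throughout.

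| Open stay starts | Next stay starts | Rule 1 | Rule 2 | Ratio |
|---|---|---|---|---|
| Day 30 | Day 60 | 218 − 30 + 1 = 189 | 59 − 30 + 1 = 30 | 6.3 |
| Day 30 | Day 45 | 189 | 44 − 30 + 1 = 15 | 12.6 |
| Day 150 | Day 165 | 218 − 150 + 1 = 69 | 164 − 150 + 1 = 15 | 4.6 |
| Day 10 | Day 180 | 218 − 10 + 1 = 209 | 179 − 10 + 1 = 170 | 1.2 |

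In the second row, if the next stay runs from Day 45 to Day 50 (6 days), the participant's total is 189 + 6 = 195 under Rule 1 and 15 + 6 = 21 under Rule 2. All 6 days of the second stay are counted twice under Rule 1.

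**Two stays, both without a discharge date,** starting Days 30 and 60. Rule 1 gives 189 + (218 − 60 + 1) = 189 + 159 = 348 days, more than the 218 days from first dose to last visit. Rule 2 gives 30 + 159 = 189.

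**Death, no later stay.**

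- Admission Day 30, last visit Day 36, death Day 45: Rule 1 gives 36 − 30 + 1 = 7; Rule 2 gives 45 − 30 + 1 = 16.
- Admission Day 100, last visit Day 103, death Day 120: Rule 1 gives 4; Rule 2 gives 21.

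**Whether another section settles it.** SAP 6.1.7.1.2 restricts date imputation to adverse events and medications. SAP 6.7 records no changes to the protocol-planned analyses. The amendment table in SAP 6.8.1 has no entry for healthcare resource utilization. The inclusion bullet decides which stays count, not when they end, and every stay above satisfies it.

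**The case against.** The strongest reply is that the two statements are a short default followed by its detail. They sit in one note with one bullet between them. The second is explicitly an ordered imputation rule, and its last step is in substance the earlier sentence. On that reading a careful programmer would apply the three steps and never produce 189 days. This is probably what was intended, but the text does not say so, and on that reading the earlier sentence adds nothing. One could also read the first sentence as meant for participants still in hospital and the second for unrecorded discharges. The text does not say that either, since the ordered rule applies to any missing discharge date.

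The objection to size stands. A reader might infer that hospital days will be several times too large or too small, or that one record will dominate an arm of about 6. The documents do not support this. They report no hospitalization, no missing discharge date and no death. The SAP gives 12 participants in total (SAP 3) without stating the split by arm. Day 218 is the last visit of a completer, so it lies near the wide end of the possible gap, and the ratio can be close to 1. In addition, 5.7.1.4 specifies a listing, with no mean, between-arm comparison or test of hospital days. With so few participants listed individually, an implausibly long stay that overlaps a later one should be visible.

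**Conclusion.** The contradiction is real, and nothing elsewhere in the SAP resolves it. It affects a record only when the discharge date is missing and there is also a later stay or a death.

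- **Later stay.** The direction is clear. A stay cannot run past the next admission, so carrying it to the last visit overstates the days and counts the later stay twice. The assumed dates give ratios from about 1.2 to 12.6; these illustrate what is possible and do not predict what will be seen.
- **Death.** The documents show only that the two rules differ. The last-visit rule is a true undercount only if the participant remained in hospital after that visit. If the participant had been discharged and died later, the death-date rule would be the one that overcounts.

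The consequence is small: an exploratory endpoint, listed and not tested, in 12 participants. It is a point of reproducibility, worth correcting because the correction is trivial.

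**What to change.** In the duration bullet of SAP 5.7.1.4, delete the sentence "If a participant does not have discharge date, last available visit date will be used", or replace it with a reference to the three-step rule below it. Only the ordered rule then applies: day before the next stay, then death date, then last visit date. Nothing is lost, because the last visit date is already the third step. The cost is one sentence in the SAP, with no new data and no added analysis.

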5.8 Interim Analyses

There is no interim analysis planned for this study.

5.9 Data Monitoring Committee (DMC)

There is no individual DMC set up for this study. Instead, an overarching Rozanolixizumab program independent DMC (PiDMC) will oversee the safety of this study by reviewing safety data at periodic data reviews in collaboration with other Rozanolixizumab studies. The timing and data required for the overarching PiDMC will be described in overarching Rozanolixizumab PiDMC charter.

